6 ENDPOINTS

6.1 Primary Endpoint

1. Freedom from recurrent ventricular arrhythmias at 6 months, defined as sustained ventricular tachycardia lasting longer than 30 seconds or a decrease in ventricular arrhythmias (defined as unifocal PVCs, couplets, non-sustained VT) to less than 5000 ventricular beats per 24 hours and identified due to clinical symptoms, device interrogation, or 24-hour ambulatory monitoring.
2. Procedural complications (death, stroke, myocardial infarction, heart failure, conduction abnormalities, pericardial effusion requiring drainage, hematoma, pseudoaneurysm)

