5 SCHEDULE OF TREATMENT AND TESTS

TABLE 1: SCHEDULE OF TREATMENTS AND TESTS:

	Baseline (within 30 days)	Procedure	Discharge	Telephone Follow-up (2 weeks +/- 3 days)	Follow-up Visit (6mo, +/- 2 weeks)
Type of visit	Office	Hospital		N/A	Office
Informed Consent	X				
Brief History & Physical	X				X
Blood Laboratory Testing: CBC, Electrolytes, BUN/Creatinine, BNP, INR, LFTs	X				X (as indicated)
TTE	X (within 3 months)				
CT/MRI (optional)	X (within 3 months, if done)				
*24-Hour Ambulatory Monitor	X (within 3 months)				X
ICD Interrogation	X				X
Ablation Procedure		X			
EKG	X				X
Medications	X	X	X	X	X
Adverse Events		X	X	X	X

*24-hour ambulatory monitoring will only be required for those undergoing ablation for frequent ventricular arrhythmia (defined as unifocal PVCs, couplets, non-sustained VT) that is causing a decline in LV ejection fraction to $\leq 40\%$.

Patients whose VT is successfully treated with standard ablation once enrolled will be placed in a registry and will continue to be followed throughout the study, adhering to the same post-procedure schedule as the patients who underwent intramural needle ablation. Patients whose VT is not inducible and no VT ablation is performed during the procedure will also be considered screen failures. No follow-up will be performed with subjects who have no VT ablation during the procedure.

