7 STUDY SUBJECTS

7.1 INCLUSION CRITERIA

1. The study will include patients with any of the following criteria: a) monomorphic ventricular tachycardia (VT); b) frequent ventricular arrhythmia (defined as unifocal PVCs, couplets, non-sustained VT) with a PVC burden $\geq 13\%$, or is causing a decline in left ventricular (LV) ejection fraction to $\leq 40\%$; or c) previous failed ablation for one or more of the criteria above.
2. ≥ 16 years of age.
3. Left ventricular (LV) ejection fraction $> 10\%$ as estimated by echocardiography, CT/MRI, contrast ventriculography, or radionuclide imaging within the past 90 days.
4. Clinical indication for catheter ablation of VT
5. Intramural ventricular arrhythmias not terminable with standard ablation once enrolled in the Intramural Needle Ablation study or previous failed ablation within 6 months prior to enrollment.
6. Ability to understand the requirements of the study and sign the informed consent form. For potential patients aged < 18 , parental consent will be required along with subject assent.
7. Able and willing to comply with all pre-, post-, and follow-up testing and requirements.
8. Projected lifespan greater than 1 year.

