8 SAMPLE SIZE

This safety and efficacy study will enroll up to 200 patients across 1 US center. This number has been determined on the basis of study feasibility and not by statistical means. In a similar trial, we have experienced a 66% screen failure rate; as such, with 200 patients enrolled, we expect to have approximately 70 evaluable patients who have undergone the INA procedure.

[figure not shown]

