10 STUDY PROCEDURES

10.1. PRE-PROCEDURE EVALUATION

Patients will be consented for the study in either the inpatient or outpatient setting. The consent will detail the use of RF energy as part of standard of care in all patients undergoing VT ablation, and INA ablation as an experimental procedure employed only if patient had an unsuccessful ablation within six months prior to enrollment or if the index ablation procedure proves unsuccessful. Unsuccessful ablation is defined as the inability to terminate ventricular arrhythmias or ventricular arrhythmias that are still inducible following ablation.

The following tests and procedures will occur before the ablation as a routine part of pre-procedural medical assessment (all done within 30 days prior to procedure unless noted below):

- Recording of patient medical history (including details of VT both clinical/ICD)
- Recording medication history (including all anti-arrhythmic drugs used and duration of use)
- Obtain β-HCG in females of child bearing age the morning of the procedure as per usual clinical practice
- Baseline assessment of arrhythmia burden and type:
 - Office/inpatient records, ICD interrogation report

- For patients being considered for PVC ablation only: 24-Hour Holter monitoring (within three months)
- Review pre-procedural imaging (within three months): MRI/CT (optional), TTE.
- Baseline laboratory, including complete blood count, standard electrolyte panel, renal function, and brain natriuretic peptide levels.
- Consent must be obtained before the VT ablation procedure.

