10.4 POST-PROCEDURE

10.4.1 POST-PROCEDURE FOLLOW UP

- All patients will be monitored to verify vascular hemostasis prior to discharge from the hospital.
- The majority of patients will receive either warfarin or a novel oral anti-coagulant (dabigatran, rivaroxaban, or apixaban) for 4-6 weeks post-procedure. Those patients with less extensive ablations may receive oral aspirin (81-325 mg daily) or clopidogrel (75 mg daily). These decisions will be made at the discretion of the primary operator per current guidelines.
- A proton pump inhibitor is recommended for any significant esophageal temperature rises noted during the procedure as determined by the treating physician. However, if the esophageal temperature is noted to have been $\geq 41.0^{\circ}\text{C}$, a proton pump inhibitor is required for a minimum of 4 weeks following the ablation procedure.
- Medication and adverse event review will be performed prior to discharge.
- Complications including vascular, stroke, heart failure, pericardial effusion, tamponade, bleeding, and death will be documented.
- The total number of episodes of VT, ATP, and shocks will be documented at all visits.

- The follow-up includes:
 - 2 weeks: Telephone follow up
 - Assessment for adverse events or recurrent arrhythmia.
 - 6 months: In-office follow up
 - History and Physical
 - Electrocardiogram
 - ICD interrogation (may be trans-telephonic)
 - Review of medications and adverse events
 - For PVC ablation patients only: 24-Hour Holter monitoring

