10.4.3 REPEAT VT ABLATION PROCEDURES

- One repeat intramural needle ablation procedure may be performed within the six-month follow-up period post procedure at the discretion of the physician and the participant will be deemed a treatment failure. Additionally, should a participant finish the six-month follow-up period and require a repeat intramural needle ablation for ventricular arrhythmias at a later date, the patient may be re-enrolled and re-consented in the trial using the same identification number. Primary and secondary endpoints in these re-enrolled patients will be re-assessed at six months post-second procedure. The maximum allowable number of intramural needle ablation procedures for any participant is two, irrespective of the timing of the second procedure.

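### Section 6.1 defines freedom from recurrence by joining a failure event and a success event with *or*, assigns neither to a patient group, and relies on a 6-month beat count that the protocol does not consistently require

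*Combined protocol and SAP*

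**What the plan says.** - **Section 6.1** gives the primary efficacy endpoint as freedom from recurrence at 6 months, "defined as sustained ventricular tachycardia lasting longer than 30 seconds or a decrease in ventricular arrhythmias" (PVCs, couplets, non-sustained VT) to under 5000 ventricular beats in 24 hours. Symptoms, device interrogation or a 24-hour recording may each serve as the source. The Protocol Summary gives only the endpoint's name.
- **Section 7.1**, criterion 1, admits patients who meet any of three conditions: (a) monomorphic VT; "b) frequent ventricular arrhythmia (defined as unifocal PVCs, couplets, non-sustained VT) with a PVC burden" of at least 13%, or with an LVEF decline to 40% or less; (c) a previous failed ablation for either.
- **Section 7.2**, exclusion 3, removes idiopathic arrhythmia only where there is neither structural heart disease nor significant LV depression.
- **Section 5, Table 1 footnote**, limits the 24-hour monitor to ablation for frequent ventricular arrhythmia, "defined as unifocal PVCs, couplets, non-sustained VT) that is causing a decline in LV ejection fraction" to 40% or less.
- **Section 10.1** lists at baseline "For patients being considered for PVC ablation only: 24-Hour Holter monitoring (within three months"), and **section 10.4.1** lists at 6 months "For PVC ablation patients only: 24-Hour Holter monitoring". Neither carries an LVEF condition.
- **Section 10.4.3** allows one repeat needle ablation within the 6 months, "at the discretion of the physician and the participant will be deemed a treatment failure".
- **Section 17** reports the endpoint as one percentage of a total study population that it does not define. **Section 8** sets the sample size by feasibility and states: "we expect to have approximately 70 evaluable patients who have undergone the INA procedure".

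**The concern.** The definition names an outcome that should count against the patient and an outcome that should count for the patient, and treats them as alternatives within one term. Neither literal reading fits the endpoint's name, so whoever scores the data must supply a rule that the protocol does not contain.

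The study is uncontrolled, unblinded and purely descriptive, so this percentage is its main efficacy result. If the rule is not fixed in advance, it could be chosen after outcomes are known. The second limb also needs a 24-hour count, and the sections that schedule that count disagree about who must have it.

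**Working it through.** **1. The two literal readings of 6.1.**
- As a definition of freedom: free if sustained VT occurs *or* the count falls below 5000. A patient with recurrent sustained VT and a count still at or above 5000 is scored free.
- As a definition of recurrence: failed if sustained VT occurs *or* the count falls below 5000. A patient without VT whose ectopy has dropped below 5000 is scored a failure.

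**2. What the other sections imply.** The count limb uses the same list of arrhythmias as criterion 1(b), and sections 10.1 and 10.4.1 reserve the Holter for PVC ablation patients. This points to the VT limb for VT patients and the count limb for ectopy patients. Two sensible rules fit that signal:
- *Own limb only*: each group is judged on its own limb.
- *VT for all, plus count*: nobody may have sustained VT, and ectopy patients must also be below 5000.

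| Treated for | Sustained VT | Below 5000 | Own limb only | VT for all, plus count |
|---|---|---|---|---|
| VT only | yes | not judged | not free | not free |
| VT only | no | not judged | free | free |
| Ectopy only | no | yes | free | free |
| Ectopy only | no | no | not free | not free |
| Ectopy only | yes | no | not free | not free |
| **Ectopy only** | **yes** | **yes** | **free** | **not free** |
| Both | no | yes | free | free |
| Both | yes | no | not free | not free |
| **Both** | **yes** | **yes** | **not assigned** | **not free** |
| **Both** | **no** | **no** | **not assigned** | **not free** |

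The one firm conflict is the ectopy-only patient with fewer than 5000 beats and sustained VT. Patients who meet both 1(a) and 1(b) are left open where their two limbs disagree. The Protocol Summary, section 10.4.3 and section 17 do not settle either case.

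**3. Is the count a real test?** A burden of 13% equals 5000 beats when total beats are 5000 / 0.13 = 38,462 per 24 hours, or 38,462 / 1,440 = 26.7 per minute. At any ordinary heart rate, a patient admitted on burden starts above 5000 and must fall to pass. That requires a 24-hour count.

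**4. Is the count required?** Take a patient with structural heart disease, a burden of at least 13% and LVEF above 40%. Criterion 1(b) admits this patient and exclusion 3 does not remove them. Sections 10.1 and 10.4.1 list a Holter for them; the Table 1 footnote does not require one. Section 6.1 does not close the gap, because it also accepts symptoms or device interrogation.

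**5. Size per patient.** The plan's own figure reproduces: 200 × (1 − 0.66) = 68, stated as about 70. One reclassified patient moves the percentage by:
- 1/70 = 1.43 points, or 1/68 = 1.47 points, if the denominator is the evaluable needle-ablation patients;
- 1/200 = 0.50 points if it is everyone enrolled.

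Section 17 does not say which denominator applies. The documents give neither the mix of indications nor the expected frequency of the bold rows, so a total effect cannot be computed.

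**The case against.** The strongest reply is that the intent is plain. The count limb repeats the wording of criterion 1(b), the Holter lines are confined to PVC ablation patients, and what is missing is a phrase such as *absence of* and one sentence of assignment. A patient in both groups would naturally have to pass both limbs, which removes the two unassigned rows and leaves one conflict that nothing in the documents suggests is common. The study has no hypothesis test, and one patient is worth about 1.4 points.

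Much of this stands. The signal is strong, and the literal readings show that the text is wrong, not how investigators would act. But the protocol never states the assignment, the ectopy-only conflict survives even on the generous view, and the footnote contradicts two other sections.

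A reader might infer more than the documents support:
- *That baseline counts are generally missing.* Section 10.1 lists a baseline Holter for all PVC patients, and a patient admitted on burden needs some recording to establish it. The exposed point is the 6-month count.
- *That many patients could already be below 5000 at baseline.* The LVEF route sets no minimum burden, but it requires frequent arrhythmia that is causing the decline. The lowest burden that section 3 links to LV recovery after ablation is 10%, which exceeds 5000 beats above 5000 / 0.10 / 1,440 = 34.7 per minute. The gap is close to theoretical.
- *That VT ended by ATP or shock within 30 seconds is unaddressed.* The 30-second threshold already excludes it, and section 10.4.1 says "The total number of episodes of VT, ATP, and shocks will be documented at all visits". Counting such episodes as failures would be a different endpoint.

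**Conclusion.** The point holds and should be fixed before outcome data are reviewed. The definition in 6.1 gives the wrong score if followed literally, no other section assigns the limbs, and the 6-month count is not securely required for PVC patients admitted on burden with LVEF above 40%. That last gap arises only if the Table 1 footnote prevails over sections 10.1 and 10.4.1.

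The effect is 1.4 to 1.5 percentage points per reclassified patient, assuming 68 to 70 evaluable patients form the denominator. The number of such patients is unknown. The table above counts types of patient, so a reader should not take its rows as shares of the sample. No test, power or sample-size figure is affected.

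**What to change.** - **Reword 6.1.** Freedom at 6 months means absence of sustained VT beyond 30 seconds and, for patients treated for PVCs, couplets or non-sustained VT (including those who also meet 1(a)), a decrease to under 5000 ventricular beats on the 6-month 24-hour recording. If the sponsor intends PVC-only patients to be judged on the count alone, 6.1 must say so before data are reviewed.
- **Cross-reference** the treatment-failure rule of section 10.4.3 in 6.1.
- **Reconcile** the Table 1 footnote with sections 10.1 and 10.4.1 so that every patient judged on the count has a required 6-month recording. State that a patient without that count is not scored free by default.
- **Name the denominator** in section 17.

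The cost is a wording amendment and one reconciled monitoring requirement. It may mean some additional 24-hour recordings, which sections 10.1 and 10.4.1 already list, and possibly a lower reported success rate.

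### VT that an ICD ends by pacing or shock within 30 seconds meets neither recurrence limb of the efficacy endpoint, so a patient with treated recurrences can be scored as free of arrhythmia

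*Combined protocol and SAP*

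**What the plan says.** The first primary endpoint in Section 6.1 is "Freedom from recurrent ventricular arrhythmias at 6 months". It has two limbs. The VT limb is "defined as sustained ventricular tachycardia lasting longer than 30 seconds". The limb for PVCs, couplets and non-sustained VT requires a fall "to less than 5000 ventricular beats per 24 hours". Events are "identified due to clinical symptoms, device interrogation, or 24-hour ambulatory monitoring". That clause names ways of finding an event; it does not add a criterion for what counts as one.

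Section 10.4.1 states: "The total number of episodes of VT, ATP, and shocks will be documented at all visits". Table 1 in Section 5 schedules ICD interrogation at baseline and at the 6-month visit. The follow-up monitor in 10.4.1 is restricted: "For PVC ablation patients only: 24-Hour Holter monitoring".

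One further failure rule stands outside Section 6. Under 10.4.3, if a repeat INA is done within the six-month follow-up, at the physician's discretion, "the participant will be deemed a treatment failure".

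The protocol summary, Section 6.2 and Section 17 do not mention ATP or shock. Section 17 reports the co-primary endpoints as percentages of the whole study population, with no test or success threshold.

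**The concern.** An ICD acts to end VT early. A patient whose VT returns after needle ablation, and whose device ends every episode within 30 seconds, has had treated recurrences, yet none of them passes a test based on duration alone. Followed as written, 6.1 can score that patient as a success.

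The efficacy percentage would then depend partly on how quickly devices respond, which says nothing about whether the needle removed the arrhythmia. Compared with an endpoint that counts treated VT, leaving it out can only raise the freedom rate. The study has a single arm, so there is no comparator in which the error could cancel. The protocol clearly expects patients with ICDs, since it schedules interrogation and asks for ATP and shock totals, but no endpoint or analysis uses them.

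**Working it through.** **1. The plan's own figure.** Section 8 expects about 70 evaluable INA patients from 200 enrolled with 66% screen failure: 200 × (1 − 0.66) = 68, which agrees. The documents give no assumed freedom rate, ICD share, recurrence rate or time to device therapy.

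**2. One patient through the rules.** Interrogation at 6 months shows three VT episodes of 15 seconds each, two ended by ATP and one by shock.

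- VT limb: no episode exceeds 30 seconds, so there is no recurrence.
- 5000-beat limb: at an assumed 200 beats per minute, each episode is 200 × 15/60 = 50 beats, and three make 150. The limit is not approached.
- Repeat INA under 10.4.3: failure only if the physician chooses to repeat the procedure within six months.

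Without a repeat INA, the patient is scored as free.

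**3. Can the 5000-beat limb close the gap?** Take full 30-second episodes at assumed rates of 120 to 250 beats per minute. Each has 60 to 125 beats. Reaching 5000 in one day needs 5000/125 = 40 to 5000/60 ≈ 83 episodes. In addition, 10.4.1 requires the follow-up monitor only for PVC ablation patients, and the footnote to Table 1 is narrower still. The limb does not close the gap.

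**4. Size, as an illustration.** Let N be the INA patients, n those with VT and an ICD, r their recurrence rate, and t the share of recurring patients whose episodes all end within 30 seconds and who have no repeat INA.

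Overstatement of freedom = n × r × t / N.

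Assume N = 70, n = 40 and r = 40%, so 16 patients recur.

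| t | Patients scored free despite treated VT | Overstatement over 70 |
|---|---|---|
| 25% | 4 | 4/70 = 5.7 points |
| 50% | 8 | 8/70 = 11.4 points |
| 75% | 12 | 12/70 = 17.1 points |

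**5. Range.** With n = 40, r from 20% to 50% and t from 25% to 75%:

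- lowest: 40 × 0.20 × 0.25 = 2 patients, 2/70 = 2.9 points
- highest: 40 × 0.50 × 0.75 = 15 patients, 15/70 = 21.4 points

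The result is proportional to n, so with n = 20 every figure halves. Each misscored patient moves the rate by 1/70 = 1.4 points.

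**The case against.** **Size.** Every driver of the size is assumed. Whether devices end VT before 30 seconds is the crux, and the documents do not address it. This stands: confidence attaches to the gap in the rule, not to its size. VT that outlasts 30 seconds before therapy succeeds still counts.

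**A subgroup denominator.** A reader might infer that reported freedom becomes 28/40 = 70%, 32/40 = 80% or 36/40 = 90% against 24/40 = 60%, a shift of 10, 20 or 30 points. Those are percentages of the assumed 40 ICD patients. Section 17 plans no such subgroup and reports over the study population, so the smaller shifts over about 70 are the relevant ones.

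**Another failure rule exists.** A reader might infer that duration is the only route to failure for a VT patient. Section 10.4.3 contradicts that, and some patients with treated recurrences will be caught by a repeat INA. The rule is discretionary and ICD therapy does not trigger it, so it is a partial safeguard.

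**Patients without an ICD.** It is tempting to say that the same arrhythmia without a device would run past 30 seconds and be counted. The documents do not support that certainty: a 15-second episode might have ended by itself.

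**Investigators may count treated VT anyway.** Some may read sustained VT as including VT that needs intervention. The sentence gives a duration and nothing else. If the wider reading is intended, it has to be written, because in an unblinded study scoring should not rest on unstated judgement.

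**Nothing turns on the rate.** The study is descriptive, its size was set by feasibility, and its only numerical stopping rule concerns safety. ATP and shock totals are collected, so the information is not lost. This limits the consequences, but the co-primary percentage is still the study's efficacy result.

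**Conclusion.** The gap holds on the current text. In a patient with an ICD, VT ended by ATP or shock within 30 seconds meets neither recurrence limb of 6.1 and can be scored as freedom, except where a discretionary repeat INA within six months makes the patient a failure. The bias runs in one direction, towards a higher freedom rate.

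Its size cannot be derived from the documents. The illustrative 6, 11 or 17 points rest on four assumptions: the study population in Section 17 is taken to be about 70 INA patients, 40 of them have VT and an ICD, 16 of those recur, and 4, 8 or 12 of the 16 have only short treated episodes and no repeat INA. The fault lies in the endpoint definition, not in data capture, and it should be corrected before the endpoint is scored.

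**What to change.** In Section 6.1, define VT recurrence for endpoint scoring as sustained VT lasting more than 30 seconds, or any VT episode for which the device delivered ATP or shock, whatever its duration. Require that the episode be confirmed as VT from the ICD interrogation already scheduled in Table 1 and 10.4.1. Bring the treatment-failure rule of 10.4.3 into the same definition, so that all routes to failure stand in one place. Report freedom under the current 30-second rule alongside, to show how much the treated episodes matter.

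The change takes a sentence or two in 6.1 and a line in Section 17. It adds no visits or patients and does not touch device programming or care. It has three costs:

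- The freedom rate will probably be less favourable.
- A reader might infer that the ATP and shock totals are enough for scoring. Totals do not show which therapy treated which episode, or whether it was delivered for VT, so episode-level review of the interrogation is needed.
- Some treated episodes that might have ended by themselves will count, which tilts the comparison between ICD and non-ICD patients the other way. The side-by-side report makes this visible.

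### Sustained-VT patients without an ICD are followed for recurrence only by symptoms and one 6-month EKG, and a single reported percentage lets silent VT count as freedom

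*Combined protocol and SAP*

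**What the plan says.** All references are to the combined protocol and SAP.

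- **Event.** Section 6.1 takes as the VT event "sustained ventricular tachycardia lasting longer than 30 seconds". It sets a duration but no rate.
- **Detection.** The same section accepts recurrence "identified due to clinical symptoms, device interrogation, or 24-hour ambulatory monitoring".
- **Eligibility.** Section 7.1 admits patients on monomorphic VT alone. No item in sections 7.1 or 7.2 mentions an ICD.
- **24-hour monitor.** The footnote to Table 1 (section 5) says "24-hour ambulatory monitoring will only be required for those undergoing ablation for frequent ventricular arrhythmia" and narrows this further to arrhythmia that has lowered LVEF to 40% or less. Section 10.4.1 lists it differently: "For PVC ablation patients only: 24-Hour Holter monitoring". Under either wording a sustained-VT patient is not covered.
- **Device data.** Table 1 and section 10.4.1 schedule ICD interrogation at 6 months. They name no substitute for a patient without a device and say nothing about device settings.
- **Other contacts.** There is a 2-week telephone call ("Assessment for adverse events or recurrent arrhythmia") and a 6-month office visit with history, physical examination and EKG. Section 10.4.1 adds "The total number of episodes of VT, ATP, and shocks will be documented at all visits", without saying how episodes are counted when there is no device.
- **Analysis.** Section 17 shows the efficacy endpoint as events out of everyone in the study. It has no breakdown by detection method and no rule for a patient whose rhythm was not monitored.

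**The concern.** One endpoint is measured in two ways within the VT group. A patient with an ICD has device records to be read at 6 months. A patient without one depends on noticing the arrhythmia and reporting it, or on being in VT during the 6-month EKG. The two groups are then pooled.

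For silent recurrences the error has one direction: a missed VT raises the freedom rate. The headline percentage therefore depends partly on how many VT patients happen to carry an ICD, which has nothing to do with the needle catheter. The design is non-randomized and section 17 plans no comparison, so nothing in the analysis offsets the error. A reader of the final report could not judge its size unless ICD status is shown.

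**Working it through.** **Plan's own figure.** Section 8 expects about 70 evaluable needle-ablation patients from 200 enrolled with 66% screen failure: 200 × (1 − 0.66) = 68. This agrees. Section 8 says the number rests on feasibility, so there is no power calculation to reproduce.

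**Routes to detection for a sustained-VT patient**

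| Route | With ICD | Without ICD |
|---|---|---|
| Symptoms, including the 2-week call | yes | yes |
| Device interrogation at 6 months | yes | no |
| 24-hour monitor at 6 months | not required | not required |
| 6-month EKG (not named in section 6.1) | yes | yes |

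**Illustration of size.** The documents supply none of these inputs, so all are assumptions: true recurrence R = 50%; detection with an ICD d = 95%; detection without an ICD s = 40-80%; share of VT patients without an ICD p = 10-40%.

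Reported freedom = 1 − R × [(1 − p) × d + p × s].

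With p = 0 this is 1 − 0.5 × 0.95 = 52.5%. The 2.5 points above the true 50% come only from the assumed 95% ICD sensitivity and must not be charged to the absence of a device. The part due to patients without an ICD is R × p × (d − s):

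| p | s | Reported freedom | Added by patients without an ICD |
|---|---|---|---|
| 10% | 80% | 53.25% | 0.5 × 0.1 × 0.15 = 0.75 points |
| 30% | 60% | 57.75% | 0.5 × 0.3 × 0.35 = 5.25 points |
| 40% | 40% | 63.5% | 0.5 × 0.4 × 0.55 = 11 points |

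If all 70 evaluable patients were VT patients, this would be about 0.5, 3.7 and 7.7 patients wrongly counted as free.

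**Second set of assumptions.** Let ICDs miss nothing, true freedom F be 40-60%, the share without an ICD q be 10-50%, and the share of their recurrences never reported m be 25-50%. The bias is (1 − F) × q × m, from 0.4 × 0.10 × 0.25 = 1 point to 0.6 × 0.50 × 0.50 = 15 points.

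**Scale.** At n = 70 and 50% freedom, the 95% confidence half-width is 1.96 × √(0.5 × 0.5 / 70) = 11.7 points.

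**Would one 24-hour monitor at 6 months help?** For k episodes at random times in 182 days, the chance that one recorded day contains an episode is 1 − (1 − 1/182)^k. This is 0.5% for k = 1, 1.6% for k = 3, 5.4% for k = 10 and 15% for k = 30.

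**The case against.** The strongest reply is that the study is single-arm, descriptive and sized on feasibility. No efficacy threshold exists for the bias to tip, and at the low end of the assumptions (0.75 points) it is trivial beside a half-width of about 12 points. Section 10.1 already collects VT history from clinical and ICD sources and an ICD interrogation report, so ICD status can probably be recovered, and section 17 does not forbid a split. All of this stands. It limits the severity and makes the remedy cheap, but the plan as written still yields one pooled figure.

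Four stronger readings are tempting, and the documents do not support them.

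- *Only an ICD can detect VT objectively.* Every followed patient has a 6-month EKG, a symptomatic recurrence can be documented clinically, and section 6.1 refers to device interrogation in general. The gap concerns silent VT between contacts.
- *ICD patients are known to miss VT below a programmed rate.* No section discusses detection zones or programming. What can be said is that no device setting is specified or recorded.
- *The plan states that undetected VT is scored as freedom.* It does not. This follows from section 6.1 together with section 17's silence on patients not monitored.
- *The missing 24-hour monitor is the main fault.* One day of recording would rarely catch sporadic sustained VT, as the figures above show.

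**Conclusion.** The concern holds for sustained-VT patients without a device. Their 6-month outcome rests on symptoms and one EKG, that of ICD patients also on device interrogation, and the single percentage hides the difference. The direction is upward for silent VT.

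The size is unknown. On assumed inputs, patients without an ICD add about 1 to 11 points (1 to 15 under the wider second set). The addition is zero if every VT patient has an ICD. A reader might take the whole gap between 50% and 53-64% in the first illustration as the cost of lacking an ICD, but 2.5 points of it come from the assumed ICD sensitivity. This should be corrected before analysis; it does not invalidate the study.

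**What to change.** 1. Record on the CRF whether each patient has an ICD and, where one is present, its lowest monitored rate. This is data capture only and asks for no change in programming.
2. In section 17, report 6-month VT freedom for all VT patients and separately for (a) those with device interrogation covering follow-up and (b) those without, labelled *not continuously monitored; symptoms and EKG only*.
3. State in section 6.1 how recurrence is established in a VT patient without a device, and whether the 6-month EKG counts.
4. Do not present a single 24-hour monitor at 6 months as closing the gap.
5. Reconcile the Table 1 footnote (monitor only where LVEF has fallen to 40% or less) with section 10.4.1 (all PVC ablation patients). Under the footnote, a patient eligible on a PVC burden of 13% or more alone would have no required beat count for the 5000-per-24-hours criterion.

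The cost is two CRF fields, one split table and a few sentences of text. The downside is smaller subgroups with less precise percentages. Keeping the all-VT figure beside the split avoids having to rest the result on ICD patients alone.
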